METHODS: Describe the procedures for all aspects of your protocol. Tell us what you are doing.

Participants will be recruited by the Principal Investigator or Study Coordinator from the inpatient and **outpatient** CF population at UAB. Following admission to UAB Hospital for a routine CF exacerbation, **or within the outpatient setting**, the Study Coordinator will discuss the study with participants and obtain written informed consent before initiating the study.

Patients will be randomly allocated in unbalanced numbers (2:1) (n = 15 ketone and n = 8 control) to receive a ketone monoester or an identical-tasting placebo, respectively, for 8 days during the course of hospitalization for treatment of acute pulmonary exacerbation (One, 60 mL bottle of either a ketone ester will be consumed twice daily (30 mL or 15.0 g per dose) (KE4, KetoneAid, Falls Church, VA; 15.0 g or placebo (PL, flavored to closely match taste of the ketone) will be administered following an overnight fast and again at 1500h.

Participants will be **asked to drink about 1 fluid ounce of the ketone or placebo supplement twice a day (once in the morning and once mid-late afternoon) for up to 7 days. Each day in the study, the participant will be asked to fast overnight for about 8 hours before drinking the first dose of ketone or placebo. Following administration of the first dose of either the ketone or placebo and on either day 5, 6, or 7 a small drop of blood will be obtained from their finger before (time 0 min) and 15, 30, 60, 90, and 120 min after drinking the supplement. On days in between visit 1 and visit 2, we will check their blood sugar before drinking the supplement and 30 minutes after they drink the supplement. We will use a commercially available ketone meter (Keto-Mojo, Napa, CA) that provides a rapid assessment of blood ketone and glucose (sugar) levels. The Keto-Mojo device requires a finger stick with a lancet, identical to those used to measure blood sugar, and uses only a small drop of blood. Patients will be educated on how to use the device and self measure ketone and blood sugar.**

Blood sampling will occur from their indwelling catheter or **venipuncture** at day 1 and at day 5, 6, or 7 before administration of the ketone or placebo. We will try to coordinate this with any blood sampling done for clinical care.

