The Keto-Mojo device requires a finger stick with a lancet, identical to those used to measure blood sugar, and uses only a small drop of blood. The device provides values within about 15 seconds following sampling. An alcohol prep will be used to cleanse the surface of the skin prior to each stick and a bandage will be applied to reduce risk of infection.

Participants will remain on all CF chronic care medications **and/or** standard exacerbation therapy (intravenous antibiotics and increased airway clearance throughout the course of the study. The study pharmacist will provide the ketone or placebo supplements by computer-generated random assignment in blocks of three participants and will have sole access to the randomization code.

Spirometry measurements, CRP, and, history/physical exam and Sputum bacteriology will be conducted at the beginning of hospitalization as part of standard of care (these results will be pulled from the medical record for study purposes. Spirometry measurements and history/physical exams will also be performed at the end of hospitalization as part of standard of care and will be pulled from the medical record for study purposes.

For outpatient subjects, these results will be pulled from the medical record and study procedures will also be performed at visit 1 and visit 2 as according to the consent

Spirometry will also be performed in addition to those for standard care just before the participant drinks the ketone supplement or placebo control and one hour after on day 1 and either day 5, 6 or 7.

Additional sputum and blood will be collected at baseline before the treatment and at patient-discharge for trial-specific readouts.

The participants will also be asked to complete the CFQR questionnaire and a food diary every night. They will also be asked to complete the symptom questionnaire on hour after receiving the morning ketone or placebo.

REQUIRED - SELECT ONE OR BOTH: Will this be a retrospective study and/or a prospective study?

Yes No * Retrospective

Yes No * Prospective

Yes No * Will the study involve the prospective collection or analysis of data, documents, or records?

Yes No * Will the study involve the prospective collection or analysis of biospecimens?

What is the expected end date of the study (including data analysis)?

* Provide the total number of subjects to be included at all sites, both retrospectively (including records) and prospectively.

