5. RESEARCH DETERMINATION

Research Determination Form

- Yes No * Is the activity a **systematic investigation**?
- Yes No * Is the activity designed to develop or contribute to **generalizable knowledge**?
- Yes No * Does the project involve obtaining information about living individuals?
- Yes No * Does the project involve an **intervention** or an **interaction** with participants?
- Yes No * Does the project involve an FDA regulated test article?
- Yes No * Is the project defined as a **clinical investigation**?

Briefly describe the proposed project, including what materials are being obtained and their sources. **If you provided this information on Page 1 (General Questions), enter "See above."**

Spirometry measurements, CRP, and, history/physical exam and Sputum bacteriology will be conducted at the beginning of hospitalization as part of standard of care (these results will be pulled from the medical record for study purposes. Spirometry measurements and history/physical exams will also be performed at the end of hospitalization as part of standard of care and will be pulled from the medical record for study purposes.

Additional spirometry, questionnaire, sputum and blood will be collected at baseline before the treatment and at patient-discharge for trial-specific readouts for out patients medical history will also be pulled from the medical record

Risk Level - FDA Regulated

* **REQUIRED: Select whether the project involves minimal risk or greater than minimal risk to participants.**
Greater than Minimal Risk

Sources of Private Information

Indicate the information that may be obtained, accessed, used, disclosed, or shared from an individual (living or deceased). Select all that apply.

- An individual's genetic tests
- Genetic tests of family members of a particular individual (including an embryo or fetus)
- Genetic manifestation of a disease or disorder in family members of a particular individual
- Any request for, or receipt of, genetic services, or participation in a clinical study which includes genetic service, by the individual or any family member of the individual
- Education records of an individual
- Alcohol or substance abuse information, including diagnosis, treatment, or referral of treatment for alcohol abuse, substance abuse, or chemical dependency

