Describe the methods used to recruit the subject (i.e., how, when). If participants without an existing relationship with study personnel will be recruited via telephone, provide a copy of the required "Phone Script Template for Recruitment of Patients from an Electronic Health Record" and complete the [IRB Training - Telephone Recruitment for Human Subject Research Participants course](#).

Participants will be recruited by the principal investigator or Study Coordinator from the inpatient and outpatient CF population at UAB. [name] is a UAB physician and part of the UAB CF Care team. He is a Sub Investigator on this project and will assist in recruiting patients. Upon admission, [name] will alert the research team of the admission and a member of the research team will contact the patient to assess interest.

Electronic Medical Record query using i2b2, Electronic Data Warehouse, or IMPACT

Other

*Describe all activities to identify and recruit prospective participants.

(For assistance with the development of a Recruitment Plan, please contact [CRSP](#).)

Select the types of data collection tools that will be used in this study. Select all that apply.

Survey/questionnaire(s) (UAB recommends using Qualtrics or RedCap for electronic surveys)

Audio or video recordings

Interview guides/scripts

Subject diaries

Mobile or web application

Electronic Medical Record query using i2b2, Electronic Data Warehouse, or IMPACT

Other

Prospective Biospecimens

What type of biospecimens will be collected? Select all that apply. NOTE: If blood will be taken for screening and/or enrollment purposes, indicate them specifically. Additionally, multiple specimens taken from the same person should be counted individually (e.g., 3 participants with 4 blood draws per participant equals 12 specimens).

Tissue

Bone marrow aspirates

Blood

How many times will blood be collected?

Number of biospecimens.

Volume of blood per draw.

[5-8 ml](#)

Describe the blood collection to include when, how often, how, and volume (in teaspoons and milliliters).

additional blood will be collected at baseline and at visit 2 s for inpatients . This will be a single draw of 5-8 ml at two timepoints.

For outpatients blood will be collected at visit 1 and visit 2

- Fecal
- Semen
- Urine
- Biopsy
- Other

Number of biospecimens.

Specify. Include number of biospecimens. NOTE: If multiple types specimens (e.g., blood, urine, etc.) are obtained from the same person, they count as one.

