If the patient can expectorate additional sputum will be collected at visit 1 and visit 2

How will biospecimens be obtained, processed, distributed, and stored?

Blood samples will be collected from participants after signing informed consent. Samples will be stored and processed in [name] laboratory ([name]) for subsequent analysis.

How will biospecimens be labeled (e.g., unique identifier, medical record number, social security number, name, date of birth)?

Specimens will be labeled with a participant code and the date of the sample. The participant code will be a randomly assigned, unique alphanumeric identifier

How will clinical data associated with the biospecimens be collected and stored?

Clinical data will be collected and stored using the same alphanumeric identifier as described above and will be entered into a secure database maintained on a firewall- and password-protected network drive

What participant identifying information will be collected and linked to the biospecimens?

Samples will be labeled with a participant code and the date of the sample. Information which would reveal the identity of a participant code number or link data to an individual will be extremely limited.

What steps will be taken to maximize the confidentiality of linked identifiers? For example, procedures could include using a password-protected computer database to link identifiers, with limited personnel knowledgeable of the password, or coded identifiers released without the ability to link to clinical data (also called "stripped" or "anonymized" biospecimens).

Confidentiality of all participants will be fully protected and investigators will only use unique identifier numbers for labeling study samples and for compiling data files. Access to participant data will be strictly limited under control of the PI. Any publication of these data will not identify the participant by name.

Describe how the above numbers were determined (e.g., provide a power analysis, explain the pilot data, or reference prior studies.

Allocation of participants in a 2:1 (ketone:placebo control) fashion in blocks of 3 was chosen because this is a pilot study designed to provide preliminary data for an extramural grant. Descriptive statistics will be calculated for all quantitative measures, including assessments of acceptability and tolerability. We will have the appropriate number of patients available to address our questions.

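### Final research sputum and blood are timed at hospital discharge in two places, and at day 5, 6 or 7 or visit 2 elsewhere

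*Protocol*

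**What the plan says.** Two statements use discharge:

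- Section 1, Methods: "Additional sputum and blood will be collected at baseline before the treatment and at patient-discharge for trial-specific readouts".
- Section 5, Research Determination: "Additional spirometry, questionnaire, sputum and blood will be collected at baseline before the treatment and at patient-discharge".

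Several others use a study day or visit 2:

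- Section 1, Methods, for research blood: "at day 1 and at day 5, 6, or 7 before administration of the ketone or placebo".
- Section 9, Prospective Biospecimens, for inpatient blood: "additional blood will be collected at baseline and at visit 2", followed by "This will be a single draw of 5-8 ml at two timepoints".
- Section 9, for outpatient blood: "For outpatients blood will be collected at visit 1 and visit 2".
- Section 9, for sputum: "If the patient can expectorate additional sputum will be collected at visit 1 and visit 2".
- Section 1, Methods, for outpatients generally: "study procedures will also be performed at visit 1 and visit 2 as according to the consent".

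The Methods also place the study spirometry on day 1 and on day 5, 6 or 7, before the drink and one hour after it. Spirometry at the end of the hospital stay is listed separately, as standard care taken from the medical record.

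**The concern.** Staff who follow the discharge sentences and staff who follow the day or visit sentences would take the final sample at different times, and the text does not say which prevails. Discharge is an event after randomization whose date depends on clinical course. Sampling then would measure participants after different amounts of supplement, some perhaps after it had ended. If the supplement affected length of stay, or if stay differed by arm for any other reason, the arms would be compared at different study days. The readouts at stake are the inflammatory markers and circulating insulin and glucose, which the data safety monitoring plan (Appendix 9, Introduction) names as secondary outcomes. A collection time is an instruction to staff in the protocol, and an analysis plan written later cannot re-time a sample.

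**Working it through.** No planned figure has to be reproduced. The check sets the statements side by side.

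1. **Two times or three?** The Methods give the full 0 to 120 minute finger-stick series at the first dose and on day 5, 6 or 7, and a shorter check on the days between visit 1 and visit 2. Section 9 describes two visits over seven days. Visit 2 is therefore probably day 5, 6 or 7, although no sentence says so. The conflict is between two times: discharge, and day 5 to 7 or visit 2.

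2. **Could the discharge sample be an extra one?** For blood, no. Section 9 allows one draw of 5–8 mL at each of two time points: 2 × 5 = 10 mL to 2 × 8 = 16 mL. Taking both a day 5 to 7 draw and a discharge draw would make three: 3 × 5 = 15 mL to 3 × 8 = 24 mL. Section 9 does not provide for that, so the two times compete for one final draw. For sputum, Section 9 likewise names only visit 1 and visit 2.

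3. **Could discharge and visit 2 be the same day?** For some inpatients they may coincide. No passage ties discharge to a study day. Section 9 uses visit 2 for inpatients expressly, so the conflict exists within the inpatient cohort. Outpatients have no discharge, yet neither discharge sentence is expressly limited to inpatients.

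4. **Which wording looks current?** Appendix 3, item 5 of the IRB's August 2021 letter, asks that the consent form describe a second sputum and blood sample on day 5, 6 or 7. The reply is that this was done. That points to leftover discharge wording, but it concerns the consent form and does not remove the sentences from Sections 1 and 5.

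5. **What follows if discharge is used?** No bound on the sampling day can be computed, because no length of stay is given. The length of supplementation is itself stated three ways: 8 days and up to 7 days in the Methods, and 5–7 days in Appendix 9. A discharge after the last day of supplementation, whichever statement applies, would give an off-supplement sample.

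**The case against.** The strongest reply is that the intended schedule is clear. Four statements about blood and sputum in Sections 1 and 9 agree on day 5 to 7 or visit 2, the IRB correspondence shows the consent form was brought to the same window, and the Methods tie outpatient procedures to that consent. Section 5 answers a prompt for a brief description and is not where staff would look for a schedule. The trial is randomized and double-blind, so variation in discharge day unrelated to arm would mainly add noise. All of this stands, and it limits the point to a correction of wording. It does not remove the discharge sentence in the Methods, which is the operative section.

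A reader might infer more than the text supports:

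- *That the comparison is biased.* This needs length of stay to differ by arm, and the document has no figure on stay.
- *That the primary outcome is mistimed.* Appendix 9 names pulmonary function as primary, but the Methods schedule study spirometry on day 5, 6 or 7. Only the summary in Section 5 puts it at discharge.
- *That the pre-dose condition for blood is contradicted.* The discharge sentence in the Methods is silent on it; the earlier Methods sentence supplies it.
- *That the preliminary marker results in Section 2 came from discharge samples.* Section 2 does not say when those samples were taken.

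**Conclusion.** The contradiction is real and should be corrected. It covers the final research sputum and blood, stated at discharge in Sections 1 and 5 and at day 5, 6 or 7 or visit 2 in Sections 1 and 9. It reaches study spirometry only if the summary in Section 5 is followed. The consequence is possible uneven timing and exposure at the final marker measurement, with a risk of bias between arms that cannot be sized from this document. The conclusion assumes that visit 2 and day 5 to 7 are one occasion, which the text implies but does not state. It also takes the blood draws in Section 9 at face value. Questionnaire timing, the length of supplementation, and which spirometry reading is primary are separate matters and add no weight here; the last can be left to the analysis plan.

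**What to change.** In the discharge sentences of Section 1 (Methods) and Section 5, replace discharge with visit 2 (day 5, 6 or 7) for sputum, blood and study spirometry, and keep the existing pre-dose condition for blood. State once that visit 2 means day 5, 6 or 7 for inpatients and outpatients alike. This uses the sampling window the protocol already gives and the one requested for the consent form.

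Record the actual study day and the number of doses taken at each final sample, including for participants already sampled. Report both by arm, and flag samples outside the window.

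The cost is a wording change in two places, one defining sentence and two recorded fields. Scheduling becomes slightly less flexible. Samples already taken cannot be re-timed, so for them only the recording and reporting helps.

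Separately, the sponsor must reconcile the three statements of supplementation length in the Methods and Appendix 9. No duration or dose is proposed here.

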25. I think I look different from others my age.....				
26. I feel bad about my physical appearance				
27. People are afraid that I may be contagious				
28. I get together with my friends a lot.....				
29. I think my coughing bothers others				
30. I feel comfortable going out at night.....				
31. I often feel lonely.....				
32. I feel healthy				
33. It is difficult to make plans for the future (for example, going to college, getting married, advancing in a job, etc.)				
34. I lead a normal life.....				

Section III. School, Work, or Daily Activities

Questions 35 through 38 are about school, work, or other daily tasks.

- 35. To what extent did you have trouble keeping up with your schoolwork, professional work, or other daily activities during the past two weeks?
36. How often were you absent from school, work, or unable to complete daily activities during the last two weeks because of your illness or treatments?
37. How often does CF get in the way of meeting your school, work, or personal goals?
38. How often does CF interfere with getting out of the house to run errands such as shopping or going to the bank?

Section IV. Symptom Difficulties

Please select a box indicating your answer.

Indicate how you have been feeling during the past two weeks.

- 39. Have you had trouble gaining weight?
40. Have you been congested?
41. Have you been coughing during the day?
42. Have you had to cough up mucus?

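### Is the CFQ-R scheduled so that it lacks a pre-dose baseline and is repeated uselessly every night?

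*Protocol*

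**What the plan says.** Three instruments are attached (section 31): the CFQ-R, a symptom questionnaire and a food diary. Their timing is given in two places.

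- Section 1, Methods: "The participants will also be asked to complete the CFQR questionnaire and a food diary every night". The next sentence puts the symptom questionnaire one hour after the morning dose.
- Section 5: "Additional spirometry, questionnaire, sputum and blood will be collected at baseline before the treatment and at patient-discharge". The questionnaire is not named.

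For outpatients, section 1 says that "study procedures will also be performed at visit 1 and visit 2 as according to the consent".

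Pre-dose timing is explicit for the other measures. Extra spirometry is done "just before the participant drinks the ketone supplement or placebo control and one hour after on day 1" and again on day 5, 6 or 7. Blood is drawn "at day 1 and at day 5, 6, or 7 before administration of the ketone or placebo". Sputum is covered by "Additional sputum and blood will be collected at baseline before the treatment and at patient-discharge for trial-specific readouts". The supplement "will be administered following an overnight fast and again at 1500h", so both daily doses precede the evening.

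The symptom section of the CFQ-R (Appendix 5, Section IV) opens with "Indicate how you have been feeling during the past two weeks".

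**The concern.** Two things look wrong. First, a two-week recall form completed every night of a study lasting about a week yields heavily overlapping answers, at a real cost to participants who may be acutely ill. Second, if the nightly forms are the only ones, the first comes after the day-1 doses, so no true baseline exists. A change score from that form would already contain part of any effect. The protocol fixes pre-dose timing for blood, spirometry and sputum but never attaches it to the CFQ-R by name.

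The point has some practical interest. The preliminary results in section 2 report a better perception of respiratory function on the CFQ-R alongside no significant spirometry effect, and section 9 says the pilot is meant to supply preliminary data for a grant. A reader will want to know which form the improvement was measured from.

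**Working it through.** The protocol gives no figure to reproduce. The check is to compare the passages and then work out the worst case.

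**Which instrument is the section 5 questionnaire?**

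- Symptom questionnaire: given one hour after the morning dose, and Appendix 6 asks how long after supplementation each symptom began. It cannot be a pre-treatment measure.
- Food diary: a daily intake record, not a two-point assessment.
- CFQ-R: asks about the preceding two weeks and can sensibly be given before treatment and at the end.

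Section 5 also groups the questionnaire with spirometry, sputum and blood, the measures that section 1 places before the first dose. Staff following section 5 would hand it out in that session.

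**Is there an end point for outpatients?** Yes. Section 1 uses visit 1 and visit 2 for outpatients, and section 9 does the same for blood and sputum. Section 9 also describes the inpatient research blood as two draws, at baseline and visit 2, which section 1 elsewhere calls baseline and discharge. Discharge and visit 2 thus serve as two labels for the same end assessment.

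**Do the sections conflict?** If the nightly phrase belongs to the food diary alone, section 1 gives the CFQ-R no time and section 5 supplies one. If it covers both, section 5 adds a pre-treatment form to the nightly ones. Either way a pre-treatment form and an end form exist.

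**Worst case: the night-1 form is used as baseline.** Inputs are a 14-day recall (Appendix 5) and a visit-2 day d of 5, 6 or 7 (section 1). Assumptions are a full effect from day 1 and forms completed in the evening.

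- Share of the window on treatment, equal weights: d/14. Night 1: 1/14 = 7%. Days 5, 6, 7: 5/14 = 36%, 6/14 = 43%, 7/14 = 50%.
- Share of the change lost: (1/14)/(d/14) = 1/d. This gives 1/5 = 20%, 1/6 = 17%, 1/7 = 14%.
- If recent days count more, the loss is larger. With linearly declining weights (14, 13, ..., 1) it is 14/60 = 23% on day 5 and 14/77 = 18% on day 7. With a half-life of 3 days it is 0.215/0.713 = 30% on day 5 and 0.215/0.834 = 26% on day 7. A half-life of 7 days gives 24% and 19%. No document supplies these weights.

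**Redundancy and burden, if forms are nightly.** Adjacent windows share 13/14 = 93% of their days. The adult form has 50 items, so 5 to 7 forms need 250 to 350 responses, against 2 x 50 = 100 for two forms. The redundancy depends on equal weights: with a 3-day half-life the newest day alone carries 21.5% of the recall weight, so successive forms would differ more.

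**What no schedule changes.** At visit 2 only 36% to 50% of the recall window is on treatment (equal weights), whenever the first form is completed. That dilution belongs to the instrument and the short study.

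**The case for a change.** The best case for a change is that the assessment schedule belongs in the protocol, that the CFQ-R has already been used to report an improvement, and that the document never names a pre-dose CFQ-R. If the nightly phrase covers only the diary, section 1 gives the form no time at all. Two reconciled sentences would cost almost nothing and need no new visit.

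Part of this stands: naming the CFQ-R in section 5 would be tidier. But it would record what the two sections already lead staff to do. Section 1 refers outpatient procedures to the consent form, which is not at hand; the IRB correspondence in Appendix 3 shows that its procedures section sets sputum and blood collection by study day, so it may also time the CFQ-R. Which form counts as baseline, and how forms completed after dosing are handled, are definitions commonly left to the SAP. Removing nightly forms, if they are in use, has its own cost: participants enrolled before and after the change would have different numbers and timings of forms.

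**Conclusion.** No change to the plan follows. This is loose wording that staff and analysts can resolve sensibly: section 5 provides for a questionnaire before treatment, the CFQ-R is the only attached instrument that fits, and visit 2 (discharge for inpatients) is the end point.

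The between-arm contrast is valid on every reading, since both arms follow the same schedule, and a comparison of visit-2 scores does not depend on the first form. The outcome is supportive only: the introduction to the data safety monitoring plan (Appendix 9) makes lung function primary, and insulin, glucose and inflammatory markers secondary. The loss of 14% to 20% (18% to 30% under the assumed recency weights) is hypothetical. It needs a night-1 baseline, a full effect from day 1 and a particular model of recall, none of which the protocol states. Even then it would weaken a change score without creating a false difference.

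The conclusion rests on reading the section 5 questionnaire as the CFQ-R, which the text supports but does not state. The differing treatment durations (8 days and up to 7 days in section 1, 5-7 days in Appendix 9) are a separate matter and must be reconciled in their own right.
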